4.3. Type and Number of Subjects

A total of 528 subjects are required including a total of 12 centres (6 centres per group) and around 44 asthma subjects per centre.

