6. STUDY TREATMENT

6.1. Treatment Assignment

The study is a trial with the study centre as the unit of randomization. Computer generated randomization schedule for centres will be provided by GlaxoSmithKline (GSK) or its designee. Once a randomization number has been assigned, it is not re-assigned. Each centre will be randomized to either ACT guided treatment group or control group (usual care group). The randomization will be stratified according to the Tier of the hospitals (Tier 3 vs. Tier 2). Assignment to a treatment will not occur, as no treatment intervention is provided for this study. Each centre will be asked to recruit 44 consecutive patients with asthma attending the practice. For the subjects who are recruited in the ACT centres, they will be treated based on the ACT score. For subjects who are recruited in the control centres, they will be treated based on doctor's subjective judgment.

The subject number will be documented in the subject's clinic notes and in the CRF.

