9.2. Sample Size Considerations

9.2.1. Sample Size Assumptions

The study will be powered to demonstrate superiority of ACT guided treatment over usual care from baseline over Week 24 in the primary endpoints.

We assume an intra-cluster correlation coefficient (ICC) of $\rho=0.01$, 29% well-control rate for usual care group, and 44% for ACT guided treatment group. It is required to have 6 centres for each treatment group and a minimum of 35 subjects for each centre (a total of 420 evaluable subjects) to achieve a power of 80% with two-sided $\alpha=0.05$. We anticipate a dropout rate of 20% and therefore planned to recruit 44 subjects in each centre (a total of 528 randomized subjects). These sample size calculations are produced based on Donner [[Donner, 1981](#)].

An ACT score ≥ 20 indicates controlled asthma. The assumed rate of subjects with an ACT score ≥ 20 for usual care group is based on a nationwide epidemiologic survey in

China [Nan, 2013], which reported a 29% asthma control rate. The rate for ACT guided treatment is assumed based on GOAL study [Bateman, 2004], which reported a 80% rate for salmeterol/fluticasone group. An additional adjustment has been made to reduce it to 44% to account for real life practice. A 15% difference between ACT guided treatment group and usual care group is considered clinically meaningful.

Study centres will be randomly assigned to the 2 groups using a computer generated randomization list. The randomization will be stratified according to the Tier of the hospitals (Tier 3 vs. Tier 2).

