9.2.2. Sample Size Sensitivity

The robustness and sensitivity of the sample size calculation has been considered in order to assess the impact on the power of the study should the observed well-control rates for the primary endpoints be higher or lower than expected. Table 2 displays the estimated sample size and power for a variety of rates with other assumptions unchanged.

Table 2 Sample Size and Power Calculation by Efficacy Rates

Well-control rate ACT guided treatment	Well-control rate usual care	Total sample size to achieve 80% power	Power if 528 subjects are enrolled
40%	27%	680	69%
40%	29%	970	54%
40%	31%	1474	39%
44%	27%	404	89%
44%	29%	528	80%
44%	31%	718	67%
48%	27%	268	98%
48%	29%	332	94%
48%	31%	422	88%

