7.1. Primary Efficacy Analyses

7.1.1. Endpoint / Variables

The ACT is a validated self-administered questionnaire utilising 5 questions to assess asthma control during the past 4 weeks on a 5-point categorical scale (1 to 5).

The total score is calculated as the sum of the scores from all 5 questions, provided all scores are non-missing; if any individual scores are missing then the overall score will be set to missing.

The primary endpoint for the study is the percentage of subjects who have an ACT total score ≥ 20 or an improvement of more than 3 points in ACT total score in at least one post-baseline assessment during the 24-week treatment period.

The calculation of percentage will base on the subjects with at least one post-baseline ACT assessment.

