7.1.2. Primary Analysis Methods

The primary endpoints will be analysed using mixed effect logistic regression. In this study, generalized linear mixed model (GLMM) will be used to control for centre as a random effect since each centre is considered as a cluster in this cluster-randomization study. The statistical model on which the inference will be based will include terms for treatment, baseline ACT total score, baseline ACT total score squared, centre, type of baseline controller (ICS alone vs. ICS/LABA), gender and age. Centre, as the unit of randomization, will be treated as a random effect. Type of baseline controller (ICS alone vs. ICS/LABA) derives from the current asthma medication record in visit 0. The results of the primary analyses will be presented as adjusted odds ratios, 2-sided 95% confidence intervals, and associated p-values comparing ACT guided treatment with usual care. The adjusted odds ratios and 95% confidence intervals will be presented by a forest plot.

The example SAS codes are as below:

```
proc glimmix data=input_data method=quad;
class invsite rndgrp blcontrol gender;
model response= rndgrp actbl actblsq blcontrol gender age /s
dist=binomial oddsratio cl link=logit;
random intercept/subject= invsite;
lsmeans rndgrp /diff cl;
run;
```

where `input_data` is the name of the input dataset and `response` is the response variable. In terms of the covariates `rndgrp`, `actbl`, `actblsq`, `blcontrol`, `gender` and `age` are variables for randomised treatment code, baseline ACT total score, baseline ACT total score squared, type of baseline controller, gender and age respectively. For random effect, `invsite` is variable for centre.

Interactions between treatment and each of the covariates will be investigated in turn, with all main effects in the model regardless of their statistical significance. Any interaction terms found to be statistically significant will be explored and if necessary results will be reported for each level of the covariate. Investigation of interactions will be confined to the primary endpoints. The effect of interactions (e.g., treatment by centre) will be assessed at the 10% level of significance.

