7.2.2. Analysis Methods

All secondary endpoints will be confined to the ITT population. The continuous efficacy endpoints will be summarized by mean, standard deviation (SD), median, minimum and maximum according to scheduled visits. Time to event endpoint will be summarized by median time, 95% confidence interval of median time, lower and upper quantiles and range.

Continuous efficacy endpoints will be analysed using analysis of covariance (ANCOVA) and adjusted for centre as a random effect.

For mean daytime and night-time symptom score and mean morning and evening PEF, the mean values will be based on the available data on the diary card over each visit assessment period. No imputations will be performed on missing data. The mean values will be considered missing if less than 14 days are recorded in each visit assessment period. A Mixed Model Repeated Measures (MMRM) will be used with covariates of treatment, centre, type of baseline controller (ICS vs. ICS/LABA), gender and age, with the centre as a random factor. The results will be presented as LS mean (SE), 95% confidence interval for LS mean, treatment difference, 95% confidence interval for treatment difference and P-value by visit.

The example SAS codes are as below:

```
proc mixed data=input_data;
class invsite rndgrp visit subjid blcontrol gender;
model endpoint=rndgrp actbl blcontrol gender age/ ddfm =kr;
random intercept/subject= invsite;
repeated visit / subject=subjid type=un;
lsmeans rndgrp*visit / cl diff e;
ods output lsmeans=lsmeans;
ods output diffs=diffs;
run;
quit;
```

where `input_data` is the name of the input dataset and `endpoint` is the endpoint variable. In terms of the covariates `rndgrp`, `actbl`, `blcontrol`, `gender` and `age` are variables for randomised treatment code, baseline ACT total score, type of baseline controller, gender and age respectively. For random effect, `invsite` is variable for centre. For repeated measures, `visit` is variable for visit number and `subjid` is variable for subject's ID.

The AQLQ(S) contains 32 items in four domains: activity limitation (11 items), symptoms (12 items), emotional function (5 items) and environmental stimuli (4 items). The following items are included in each of the 4 domains:

- Symptoms: 6, 8, 10, 12, 14, 16, 18, 20, 22, 24, 29, 30
- Activity Limitation: 1, 2, 3, 4, 5, 11, 19, 25, 28, 31, 32
- Emotional Function: 7, 13, 15, 21, 27
- Environmental Stimuli: 9, 17, 23, 26

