The response format consists of a seven-point scale where a value of 1 indicates “total impairment” and a value of 7 indicates “no impairment”. The total AQLQ(S) score is the mean of all 32 items in the questionnaire and each individual domain score is calculated as the mean of the items within that domain. Hence, the total and domain scores are also each defined on a range from 1 to 7 with higher scores indicating a higher quality of life.

For the total AQLQ(S) score, the score for a subject at any time point will only be calculated if at least 90% of the questions were answered (calculated as the mean of those non-missing questions). If fewer than 90% of the questions were answered then the mean score for that subject at that time point will be considered missing.

For each individual domain of the AQLQ(S) score, the score for a subject at any time point will only be calculated if at least 90% of the questions for that domain were answered (calculated as the mean of those non-missing questions). If fewer than 90% of the questions were answered for that domain then the mean score for that subject and domain at that time point will be considered missing.

The analysis of changing from baseline to the end of study in FEV1 and AQLQ(S) score will only include those who complete the study and change from baseline will be calculated as the difference between baseline visit and Visit 6.

For FEV1 and AQLQ(S) changing from baseline, a mixed model will be used with covariates of treatment, centre, type of baseline controller (ICS vs. ICS/LABA), gender and age, with the centre as a random factor. The results will be presented as LS mean (SE), 95% confidence interval for LS mean, treatment difference, 95% confidence interval for treatment difference

The example SAS codes are as below:

```
proc mixed data=input_data;
class invsite rndgrp blcontrol gender;
```

```

model epchbl=rndgrp actbl blcontrol gender age/ ddfm =kr;
random intercept/subject= invsite;
lsmeans rndgrp/ cl diff e;
ods output lsmeans=lsmeans;
ods output diffs=diffs;
run;
quit;

```

where `input_data` is the name of the input dataset and `epchbl` is the endpoint variable changing from baseline. In terms of the covariates `rndgrp`, `actbl`, `blcontrol`, `gender` and `age` are variables for randomised treatment code, baseline ACT total score, type of baseline controller, gender and age respectively. For random effect, `invsite` is variable for centre.

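### The stated 80% power makes no allowance for having only 12 randomised centres; on 10 between-centre df it is about 71-73% at 35 evaluable per centre, and the SAP names no df for the primary test

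*Protocol*

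**What the plan says.** Protocol 9.2.1 assumes ICC 0.01, a 29% control rate under usual care and 44% under ACT guidance, two-sided alpha 0.05 and 80% power. It concludes: "It is required to have 6 centres for each treatment group and a minimum of 35 subjects for each centre". Enrolment is set at 44 per centre to allow for 20% dropout. Section 4.3 gives the same design: "A total of 528 subjects are required including a total of 12 centres (6 centres per group) and around 44 asthma subjects per centre".

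Protocol 9.2.2 then varies the two rates: "Table 2 displays the estimated sample size and power for a variety of rates with other assumptions unchanged". The 44% versus 29% row shows 528 subjects and 80%.

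Protocol 6.1 makes the level of allocation explicit: "The study is a trial with the study centre as the unit of randomization".

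SAP 7.1.2 fits a logistic mixed model by quadrature with a random intercept for centre. Its fixed terms are treatment, baseline ACT and its square, baseline controller, gender and age. The model options are "dist=binomial oddsratio cl link=logit"; neither code nor text names a degrees-of-freedom method. The SAP's PROC MIXED models do carry one: the diary endpoints ("model endpoint=rndgrp actbl blcontrol gender age/ ddfm =kr"), FEV1 and AQLQ(S) ("model epchbl=rndgrp actbl blcontrol gender age/ ddfm =kr"), and the repeated-measures model for ACT change in 7.1.3.

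**The concern.** A design effect inflates the variance for correlation within centres. It does not account for the between-centre variance having to be estimated from very few centres. Apart from treatment, every fixed term in the primary model is a subject-level characteristic, so 12 centres less 2 arms leaves 10 df for the treatment comparison.

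The power statement and the analysis therefore pull against each other. If the primary test uses a large-sample reference, the stated power is about right but the 5% level is exceeded. If it uses 10 df, the level is held at the planned ICC but the stated power is not reached at 35 per centre. The SAP leaves open which applies, although the primary p-value and confidence interval depend on it.

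**Working it through.** **Inputs** (Protocol 9.2.1): p1 = 0.44, p2 = 0.29, difference 0.15, ICC 0.01, 6 centres per arm, m = 35 evaluable per centre, two-sided alpha 0.05, 20% dropout.

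**Reproducing the stated 80%**

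- Design effect = 1 + (35 - 1) × 0.01 = 1.34.
- p1q1 + p2q2 = 0.2464 + 0.2059 = 0.4523.
- Noncentrality = 0.15 / sqrt(0.4523 × 1.34 / (6 × 35)) = 2.792.
- Normal power = P(Z > 1.96 - 2.792) = 79.7%.

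A pooled null variance gives 79.0%. A continuity correction gives 75.5% and does not fit.

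**Same noncentrality on 10 df.** Power = P(|t'(10, 2.792)| > 2.228) = 71.1%. With design effects 1.39 and 1.43 at m = 40 and 44:

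| Evaluable per centre | 35 | 40 | 44 |
|---|---|---|---|
| Normal quantiles | 79.7% | 83.4% | 85.8% |
| Centre-level t, 10 df | 71.1% | 75.2% | 78.0% |
| Random-intercept logistic on t(10), simulated | 72-73% | 77-78% | 80% |

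The simulation used a treatment-only logistic model fitted by 21-point Gauss-Hermite quadrature, Wald tests, 6 + 6 equal centres and 10,000 replicates per cell (standard error about 0.45 points for power and 0.25 for type I error). Ranges cover beta-binomial and logit-normal centre effects. A separate simulation of 2,500 runs gave 73.9% at 35 per centre.

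**Table 2.** Sample size = 2 × (1.96 + 0.8416)² × (p1q1 + p2q2) / d² × 1.34 / 0.8, where d is the difference in rates. Powers are at 35 per centre.

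| Rates | Stated N | Recomputed N | Stated N / 44 (centres) | Stated power | Normal | t(10) | Logistic on t(10), simulated |
|---|---|---|---|---|---|---|---|
| 40 v 27 | 680 | 680.1 | 15.5 | 69 | 69.2 | 60.3 | 61 |
| 40 v 29 | 970 | 969.0 | 22.0 | 54 | 54.1 | 46.2 | 46 |
| 40 v 31 | 1474 | 1473.4 | 33.5 | 39 | 38.7 | 32.8 | 33 |
| 44 v 27 | 404 | 403.5 | 9.2 | 89 | 89.2 | 82.1 | 83 |
| 44 v 29 | 528 | 528.6 | 12.0 | 80 | 79.7 | 71.1 | 72 |
| 44 v 31 | 718 | 716.2 | 16.3 | 67 | 67.0 | 58.1 | 59 |
| 48 v 27 | 268 | 266.3 | 6.1 | 98 | 97.6 | 94.2 | 95 |
| 48 v 29 | 332 | 331.8 | 7.5 | 94 | 94.1 | 88.7 | 90 |
| 48 v 31 | 422 | 421.7 | 9.6 | 88 | 87.8 | 80.4 | 82 |

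All nine stated powers match the normal calculation after rounding. The sample sizes match only if the design effect stays at 1.34, which means 35 evaluable per centre in every row and a changing number of centres.

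**Type I error**, simulated at 35 per centre with a 29% rate in both arms:

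| ICC | 0.005 | 0.01 | 0.02 | 0.03 |
|---|---|---|---|---|
| Logistic, large-sample | 5.5-5.8% | 6.4-6.8% | 8.0-8.1% | 9.1-9.2% |
| Logistic, t(10) | 2.8-3.0% | 3.4-3.8% | 4.7-4.9% | 5.7% |

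The centre-level t-test stayed at 4.6-5.4% throughout. The large-sample logistic test had 80-81% power at 35 per centre. The centre variance was estimated as zero in 45-46% of null replicates at 35 per centre. It cannot go below zero, so the standard error has a floor, which helps explain why t(10) is conservative at low ICC.

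**The case against.** The sums are correct on their own basis, and the protocol cites its cluster method, so this is a choice of approximation and not a slip. That is fair. The fault is that 80% power and a 5% level are claimed together at 35 per centre, and the design does not deliver both.

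Thirty-five is a minimum. SAP 7.1.1 says: "The calculation of percentage will base on the subjects with at least one post-baseline ACT assessment". A subject who leaves after the Week 4 visit still counts, so 20% dropout need not reduce 44 to 35. This stands, and at 44 the gap shrinks to 0-2 points. But 9.2.1 itself ties 80% to 35.

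The planned model adjusts for baseline ACT, which is plausibly prognostic for an ACT-based endpoint. In the closed-form calculation, a variance reduction of about 19% at 35 per centre, 11% at 40 or 5% at 44 would restore 80% on 10 df. That is possible, but the plan claims no gain and gives no figure for one.

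The t(10) reference is conservative at the planned ICC, so part of the loss comes from that choice. A critical value tuned to exactly 5% at ICC 0.01 (2.08-2.11) would give 76-77%. It requires the true ICC to be known, and it is still below 80%. Nor is 10 the only defensible df: adding the hospital-tier stratum would leave 9, with closed-form power of about 70%.

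The 6-7% type I error applies only if a large-sample reference is used, which the SAP does not state. It does not exclude it either, and that is the gap. Finally, the assumed rates refer to ACT of at least 20, while the endpoint is wider. All figures here are conditional on the plan's own rates.

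**Conclusion.** The concern holds. At 35 evaluable per centre, power on 10 between-centre df is 71% (centre-level t) to about 73% (random-intercept logistic), some 7-9 points below the stated 80%. At 40 per centre it is 75-78%, and at 44 it is 78-80%. The 80% is reached at 35 only with a large-sample reference, whose type I error is about 6-7% at ICC 0.01 and about 9% at ICC 0.03.

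This rests on the plan's rates and ICC, equal centre sizes and no covariate gain. The power column of Table 2 is overstated for the same reason, by about 4 to 9 points in the closed form. The table also does not tell the reader that its sample sizes imply between 6.1 and 33.5 centres. The point should be fixed. It does not invalidate the design.

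**What to change.** 1. In Protocol 9.2.1, restate power as about 71% at 35 evaluable per centre, 75% at 40 and 78% at 44, labelled as unadjusted on 10 between-centre df. Optionally add that the unadjusted random-intercept logistic model gives about 73, 77 and 80%, and that no covariate gain is claimed.
2. In Table 2, restate the power column on the same basis: 60, 46, 33, 82, 71, 58, 94, 89, 80. Label the sample-size column as normal-quantile figures that hold 35 evaluable per centre and vary the number of centres, or recompute it on a stated basis. The 44% versus 29% row should no longer show 528 subjects as giving 80%.
3. In SAP 7.1.2, prespecify a t reference with 10 df (12 centres minus 2 arms) for the primary treatment p-value and 95% confidence interval, and set it explicitly in the code. Add a centre-level t-test as a sensitivity analysis.

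The cost is wording in two protocol sections, one SAP sentence and one code option, with no extra patients. The downsides are a less favourable stated power, a confidence interval about 14% wider than a large-sample one (2.228 / 1.96 = 1.137), and a somewhat conservative test (about 3-4% type I error at ICC 0.005-0.01).

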9.2.2. Sample Size Sensitivity

The robustness and sensitivity of the sample size calculation has been considered in order to assess the impact on the power of the study should the observed well-control rates for the primary endpoints be higher or lower than expected. Table 2 displays the estimated sample size and power for a variety of rates with other assumptions unchanged.

Table 2 Sample Size and Power Calculation by Efficacy Rates

Well-control rate ACT guided treatment	Well-control rate usual care	Total sample size to achieve 80% power	Power if 528 subjects are enrolled
40%	27%	680	69%
40%	29%	970	54%
40%	31%	1474	39%
44%	27%	404	89%
44%	29%	528	80%
44%	31%	718	67%
48%	27%	268	98%
48%	29%	332	94%
48%	31%	422	88%

9.2.3. Sample Size Re-estimation or Adjustment

No sample size re-estimation is currently planned for this study. However, if during the course of the study, new information becomes available about clinically meaningful differences for the primary endpoints, a sample size re-estimation may be conducted. Full details of the procedure used would be specified in the reporting and analysis plan (RAP) and any subsequent change to the target sample size would be documented in a protocol amendment.

9.3. Data Analysis Considerations

All statistical analyses will be conducted by GSK or its designee.

In general, descriptive statistics including the number of observations, mean, standard deviation (SD), median, minimum and maximum will be provided for continuous data, frequency counts and percentages will be used in tabulation for categorical variables. Unless specified otherwise, the percentage calculation will not take the missing values into account.

If not specified otherwise, all data will be summarized/listed as observed. Missing values will not be imputed.

All tests will be two-tailed, the general two-sided significance level will be $\alpha=0.05$.

A complete description of data handling rules and planned statistical analyses are provided in a separate RAP. The RAP will be finalized before the database lock.

9.3.1. Analysis Populations

Three populations are defined for this study.

- Intent-to-Treat (ITT) Population: all subjects who signed informed consent form, were randomised and who had at least one post-baseline assessment. The ITT population will be the primary population of interest.
- Per Protocol (PP) Population: all subjects in the ITT population with no major protocol deviations and with $\geq 80\%$ treatment compliance and diary compliance. The PP population will not be analyzed if this population comprises more than 95% or

less than 50% of the ITT population. Only the primary efficacy variables will be analyzed using the PP population.

- Safety Population: all subjects who are enrolled into the study and who have at least one DRC assessment.

9.3.2. Consideration on Missing Data Handling

Missing values will not be considered when calculating the ACT score for primary endpoint, symptom score and/or PEF over 24-week treatment period. If not specified otherwise, missing values will not be imputed.

9.3.3. Interim Analysis

There are no interim analyses planned for this study.

9.4. Key Elements of Analysis Plan

All hypothesis tests and confidence intervals will be two-sided. Except where otherwise stated, the estimation of treatment effect will be adjusted for the effects of centre, type of baseline controller (ICS alone vs. ICS/LABA), gender, and age. Centre, as the unit of randomization, will be treated as a random effect.

All efficacy measures over the course of the study will be presented and summarised in graphs and tables. Continuous data will be summarised by means, standard deviations, medians, minimum and maximum; categorical data will be summarised by counts and percentages.

All outcomes will be pertained to the individual participant's level and the analysis model will be adjusted for the effect of centre (cluster).

